
 To assess if age, time since last aP vaccination (prior to study entry), or other baseline demographics have a differential response to BPZE1 or Boostrix at Day 29 (BPZE1, BPZE1 + Boostrix, Boostrix). 	
 BPZE1, BPZE1 + Boostrix, and Boostrix induction of serum immunity (IgA, IgG) by age, time since last aP vaccination (prior to study entry), or other baseline demographics at Day 29 (tested independently by treatment group).

 To assess if baseline antibody values, by baseline quantile, have variable serum immunity responses at Day 29 when BPZE1 is given alone or with Boostrix or Boostrix alone (BPZE1, BPZE1 + Boostrix, Boostrix). 	
 BPZE1, BPZE1 + Boostrix and Boostrix induction of serum immunity (IgA, IgG) at Day 29 by baseline quantile (tested independently by treatment group).

 To demonstrate that BPZE1 (BPZE1, BPZE1 + Boostrix) induces a measurable functional antibody response (subset of subjects) at Day 29; and to assess whether there is similar magnitude as that seen with Boostrix (BPZE1 vs BPZE1 + Boostrix vs Boostrix). 	
 BPZE1 and BPZE1 + Boostrix induction of measurable functional antibody (subset of subjects) compared with Boostrix at Day 29 (tested independently by treatment group).

 To assess for seroconversion at Days 29 and 85 (BPZE1, BPZE1 + Boostrix, Boostrix). Additional combinations of antibody response (WCE, PT, FHA, PRN, and any additional anti-pertussis antibodies) may also be tested. 	
 Seroconversion rate for serum immunity (IgA, IgG) defined as a 2-fold increase over baseline value; or a 4-fold increase over the lower limit of assay detection (whenever the baseline value falls below the lower limit of assay detection) at Days 29 and 85 (tested independently by treatment group and day).

 To assess reverse cumulative distribution curves for immune responses (IgA and IgG) at Day 29. 	
 Reverse cumulative distribution curves of GMT at Day 29 by treatment group.
Safety	
NOTE: Subjects participating in the substudy will be evaluated for safety endpoints in a separate evaluation after Day 85 re-vaccination/attenuated challenge.	
Secondary objectives	Secondary endpoints

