
 To describe reactogenicity events during the 7 days following any study vaccination. Primary and re-vaccination/attenuated challenge (substudy subjects) to be described separately, by treatment group. Reactogenicity will be classified by local, nasal/respiratory, and systemic. 	
 Maximum daily severity during the 7 days following study vaccination (by treatment group). Incidence by toxicity grade during the 7 days following study vaccination (by treatment group). Mean response (for any measurements) and duration during the 7 days following study vaccination (by treatment group).

 To describe (severity and relationship to study vaccination) all AEs through 28 days following any study vaccination. Primary and re-vaccination/attenuated challenge (substudy subjects) to be described separately and by treatment group. 	
 All AEs through 28 days following study vaccination by severity and relationship to study vaccination (by treatment group).

 To describe (severity and relationship to study vaccination) any medically attended AE (MAAE) through 84 days following any study vaccination. Primary and re-vaccination/attenuated challenge to be described separately and by treatment group. 	
 All MAAEs through 84 days following study vaccination by severity and relationship to study vaccination, and by time since study vaccination (by treatment group).

 To describe any AE of special interest (AESI) and SAE through Day 169/EOS including relationship to study vaccination. 	
 All AESIs and SAEs through Day 169/EOS by severity and relationship to study vaccination, and by time since study vaccination (by treatment group).

 To describe any severe acute respiratory syndrome coronavirus 2 (SARS-CoV-2) infection or AESI associated with COVID-19 disease if the COVID-19 pandemic remains ongoing in the region or if there are mass vaccinations using a COVID-19 vaccine during study conduct. 	
 Incidence of SARS-CoV-2 infections or AESIs associated with COVID-19 disease by severity, and by time since study vaccination (by treatment group).

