7.4.3.3 Analyses of Secondary Safety Endpoints

The number and percentage of subjects will be summarized for each solicited AE by timepoint, severity grade, and treatment group. Additionally, solicited AEs will be analysed by taking the maximum severity through 7 days following any study vaccination to summarize the frequency and percentage of subjects reporting each local [if applicable; after IM injection only], nasal/respiratory, or systemic event. Mean response (for any measurement) and duration through 7 days following any study vaccination will be summarized daily using descriptive statistics. Solicited AEs will be reported separately following study vaccination on Day 85 in the substudy.

Adverse events will be coded by preferred term and system organ class using the latest version of MedDRA.

The following unsolicited AEs will be summarized as number and percentage of subjects reporting at least 1 event in each preferred term and system organ class and cross-tabulated by severity and relationship to study vaccination.

- All AEs through 28 days following first study vaccination and following re-vaccination/attenuated challenge (substudy) by severity and relationship to study vaccination, and by treatment group.
- All MAAEs through 84 days following first study vaccination and re-vaccination/attenuated challenge (substudy) by treatment group by severity and relationship to study vaccination, and by treatment group and time since study vaccination.
- All AESIs and SAEs through Day 169/EOS by treatment group by severity and relationship to study vaccination, and by treatment group and time since study vaccination.

Serious AEs will be summarized by detailed listing showing the event description, preferred term and system organ class, relevant dates (study vaccinations and AEs), severity, relatedness, and outcome for each event. Any SAE considered related to BPZE1 will be classified as a SUSAR.

The number and percentage of subjects with SARS-CoV-2 infections or AESIs associated with COVID-19 infection or SARs-CoV-2 vaccine-related events will be summarized, if the COVID-19 pandemic remains ongoing in the region or if there are mass vaccinations using a COVID-19 vaccine during study conduct.

The number and percentage of subjects with colonization or clearance by real-time PCR or *B. pertussis* culture following study vaccination (subsets of subjects) will be summarized over time using the methods outlined in Section 7.4.2 for proportions.

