Secondary safety endpoints following re-vaccination/attenuated challenge for the optional substudy will be analysed in a similar fashion as the secondary safety endpoints for the main study.

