13.1 Appendix: Schedule of Events

Table 13-1 **Schedule of Events**

Subject Population	Screening		Treatment Period							EOS	
	All Subjects	All Subjects	Safety Lead-In Subjects ONLY	All Subjects	Subjects NOT in Substudy	Subjects Participating in Substudy ONLY ^d			All Subjects		
Study Visit	Screening	V1	S1 ^b	V2	V3 ^c	SSV3	SSV4	SSV5	SSV6	Unscheduled ^e	EOS/Early Termination
Study Day	-30 to 1 ^a	1	8	29	85	85	92	99	113	-	169
Window allowance	30	0	+3	+7	+14	+20	+3	+2	+7	-	+30
Informed consent	X					X ^{f,g}					
Inclusion/exclusion criteria	X	X ^{f,g}				X ^{f,g}					
Demographic and baseline data ^h	X										
Medical history ⁱ	X	X ^{f,g}									
Concomitant medication ^j	X	X ^g	X	X	X ^k	X ^g	X	X	X	X ^k	X ^k
Concomitant vaccines ^l	X	X ^g	X	X	X	X ^g	X	X	X	X	X
Targeted physical examination ^m	X	X ^g	X	X	X	X ^g	X	X	X	X	X
Vital sign measurements ⁿ	X	X ^g				X ^g				X	
Urine pregnancy test ^o	X	X ^g				X ^g				X	
SARS-CoV-2 test for active infection (within 72 hrs prior to vaccination) ^p		X				X					
Study vaccination ^q		X				X					
Immediate reactogenicity		X ^r				X ^r					
Subject diary dispensed ^s		X				X					

Subject Population	Screening		Treatment Period								EOS
	All Subjects	All Subjects	Safety Lead-In Subjects ONLY	All Subjects	Subjects NOT in Substudy	Subjects Participating in Substudy ONLY ^d				All Subjects	
Study Visit	Screening	V1	S1 ^b	V2	V3 ^c	SSV3	SSV4	SSV5	SSV6	Unscheduled ^e	EOS/Early Termination
Study Day	-30 to 1 ^a	1	8	29	85	85	92	99	113	-	169
Window allowance	30	0	+3	+7	+14	+20	+3	+2	+7	-	+30
Subject diary reviewed ^f			X	X			X			X	
Nasal sampling for immunogenicity laboratory tests		X ^g		X	X	X ^g			X		X
Mid-turbinete/nasopharyngeal sampling for B. pertussis culture or PCR			X	X ^u	X ^u		X	X			
Blood sampling for immunogenicity laboratory tests		X ^g		X	X	X			X		X
Blood sampling for cellular-mediated Th1 and Th2 responses		X ^b	X			X ^v			X ^v		
Any TEAE (following most recent vaccination)		X	X	X		X	X	X	X	X	
Any MAAEW, AESI, or SAE (following first vaccination)		X	X	X	X	X	X	X	X	X	X
EOS form											X

^a Screening visit may occur on Day 1 prior to study vaccination.

- ^b Safety lead-in subjects (only) to complete procedures listed under Study Visit S1; PBMCs to be collected in a subset of subjects.

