Note: Grade 0 will be the classification if the observation is less than a Grade 1. Any grade 3 reactogenicity event that leads to an unscheduled visit to a healthcare provider will be recorded as an MAAE.

^a Temperature may be oral, tympanic, or noncontact (clinic only). Temperature greater than 40.0 °C (104.0 °F) is considered an SAE and subjects should seek medical attention immediately.

Source: Adapted from DAIDS Version 2.1, 2017.

9.2.Unsolicited Adverse Events

Unsolicited AEs will be coded according to Medical Dictionary for Regulatory Activities (MedDRA) latest version. Unless otherwise specified, unsolicited AEs will be summarized by System Organ Class (SOC), FDA Medical Query (FMQ) and Preferred Term (PT), with SOCs sorted in the alphabetical order and PTs within each SOC in descending order of subject incidence.

TEAE is defined as an AE that starts or an existing AE that worsens on or after the date of vaccination. AEs will be summarized by treatment groups, age group, and main study and substudy separately. In general AEs will be summarized from Day 1 to end of study for overall and subjects in substudy. AEs from Day 85 to end of study for subjects in substudy will be summarized separately. Between screening and Day 1, AEs will be collected if classified as SAEs or if considered related to study procedure or study involvement. All AEs regardless of causality will be recorded for 28 days after any vaccination/challenge and summarized. All AESI and SAE will be recorded and summarized from the time of vaccination to Day 169/EOS. All MAAEs occurring through 84 days following any vaccination (and through EOS) will be recorded and summarized.

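### The Day 1-to-end-of-study by-arm safety summaries in SAP 9.2 and 9.2.1 are not cut at the Day 85 BPZE1 dose, so post-challenge events in Boostrix-arm substudy children also count in the Boostrix column

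*Protocol*

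**What the plan says.** **Provisions that separate the two vaccinations.** The note above the secondary safety endpoints in Protocol 2.2 reads "Subjects participating in the substudy will be evaluated for safety endpoints in a separate evaluation after Day 85 re-vaccination/attenuated challenge". The MAAE row there adds "Primary and re-vaccination/attenuated challenge to be described separately and by treatment group", and the reactogenicity and 28-day AE rows have equivalent text. Protocol 7.4.3.3 ends with "Secondary safety endpoints following re-vaccination/attenuated challenge for the optional substudy will be analysed in a similar fashion" as those of the main study. The opening paragraph of SAP 9 says all safety summaries are shown separately for the first vaccination and for the re-vaccination. SAP 9.2 gives substudy children their own summary from Day 85 to end of study.

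**Provisions that run across Day 85.** The SAE/AESI endpoint in Protocol 2.2 is "All AESIs and SAEs through Day 169/EOS by severity and relationship to study vaccination, and by time since study vaccination (by treatment group", with no clause splitting the two vaccinations. The matching bullet in Protocol 7.4.3.3 is "All AESIs and SAEs through Day 169/EOS by treatment group by severity and relationship to study vaccination", again without the split that the AE and MAAE bullets carry. SAP 9.2 says "In general AEs will be summarized from Day 1 to end of study for overall and subjects in substudy" and "All AESI and SAE will be recorded and summarized from the time of vaccination to Day 169/EOS", and extends the MAAE summary to end of study. In the SAP 9.2.1 overview one TEAE row is limited to the 28 days after Day 1. The rows for any TEAE, serious TEAEs, AESIs and MAAEs carry no time limit.

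**Classification and precedence.** SAP 4.3.1 assigns children in the safety set by the vaccine they actually received and does not mention a second, different vaccine. SAP 1 makes the SAP govern where it and the protocol disagree.

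**The concern.** Every substudy participant receives BPZE1 on Day 85, whatever was given on Day 1 (Protocol 3.1.1). From then on, a Boostrix-arm participant is no longer a child exposed to Boostrix alone. A by-arm table that continues to Day 169 without a cut places that child's later events in the Boostrix column. It also places events after a second BPZE1 dose in the BPZE1 columns, although the trial sets out to describe a single dose.

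Protocol 3.1 describes this as the first BPZE1 study in school-age children. SAEs are likely to be few, so one event in the wrong column could change how the by-arm comparison reads. The breakdown by time since vaccination has a related weakness: counted from Day 1, an event shortly after the challenge would look remote from any vaccination.

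**Working it through.** The plan gives no figure to reproduce here. The check has two parts: a comparison of the rules, and a calculation of how much follow-up is affected.

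**1. Which windows cross Day 85 after the first vaccination**

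- All AEs: 28 days, so Day 1 + 28 = Day 29. Does not cross.
- MAAEs under the protocol: 84 days, so Day 1 + 84 = Day 85. Closes at the challenge. Under SAP 9.2 they are also summarised to end of study, so they cross.
- SAEs and AESIs: to Day 169, which is 169 − 85 = 84 days past the planned challenge. Cross.
- The general Day 1-to-end-of-study AE summary in SAP 9.2 and the unrestricted overview rows in SAP 9.2.1. Cross.

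**2. Whether a rule cuts the crossing tables**

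- The separate Day 85-to-end-of-study summary in SAP 9.2 is an additional table. Nothing says its events leave the Day 1-to-end-of-study table.
- The opening of SAP 9 asks for separate presentation by vaccination. SAP 9.2 also refers to separate main-study and substudy summaries, but does not say that participants leave the main-study tables at the Day 85 dose. The next sentence of SAP 9.2 then defines an overall summary running to end of study. The two instructions sit in the same governing document, so the precedence rule in SAP 1 does not settle the conflict.
- The separate-evaluation note in Protocol 2.2 and the closing sentence of Protocol 7.4.3.3 say what is added after the challenge. Neither says that the first-vaccination evaluation stops there.

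**3. The column.** For a child given Boostrix on Day 1 and BPZE1 on Day 85, classification by the vaccine actually received has no defined answer. By-arm presentation leaves the child under Boostrix.

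**4. The clock.** Time since vaccination has no stated reference dose. For an event on Day 88:

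- from Day 1: 88 − 1 = 87 days;
- from a Day 85 challenge: 88 − 85 = 3 days.

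**5. Share of Boostrix-arm follow-up that comes after BPZE1**

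Inputs: 120 children per arm (Protocol Table 3-1); planned follow-up of 169 − 1 = 168 days; challenge on Day 85, or Day 105 if deferred by the permitted 20 days (Protocol 3.1.1). The number m of Boostrix children who join is an assumption. Only the overall cap of 120 is given, and 40 corresponds to a full substudy with even uptake. Full follow-up to Day 169 is also assumed.

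Share = m × (169 − challenge day) / (120 × 168), with denominator 20,160 child-days.

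| m (assumed) | Challenge day | Child-days after BPZE1 | Share |
|---|---|---|---|
| 20 | 85 | 20 × 84 = 1,680 | 8.3% |
| 40 | 85 | 40 × 84 = 3,360 | 16.7% |
| 60 | 85 | 60 × 84 = 5,040 | 25.0% |
| 40 | 105 | 40 × 64 = 2,560 | 12.7% |

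The plan tabulates children with events, not rates per child-day. These shares show the scale of mixed exposure and are not a planned statistic.

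**The case against.** The strongest reply is that the plan already separates the periods. The note in Protocol 2.2 is not limited by event type, Protocol 7.4.3.3 carries the secondary safety analyses over to the post-challenge period, and SAP 9 and 9.2 both provide a separate summary. A reader might infer that there is no Day 85 cut at all. The documents do not support that: post-challenge events will be visible in a table of their own. What stands is that the same events also stay in the by-arm table running from Day 1.

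A reader might also infer that SAEs and AESIs are the only events affected. That fails because SAP 9.2 carries MAAEs to end of study and SAP 9.2.1 has unrestricted TEAE rows.

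Nor does Table 13-1 show that time will be counted from Day 1. Its row label "AESI, or SAE (following first vaccination" says when events are collected and does not define an analysis variable. The reference dose is simply unstated.

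It would go too far to say that a BPZE1 reaction could pass unnoticed as a Boostrix event. SAE listings must show vaccination and event dates, any SAE judged related to BPZE1 is classified as a SUSAR (Protocol 7.4.3.3, SAP 9.2.4), and any vaccine-related SAE triggers a pause and safety committee review (Protocol 6.5). AESIs here are confined to COVID-19 infection or vaccination symptoms, so that part of the table says little about BPZE1 harm.

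Finally, a cumulative table beside a post-challenge table is not an error in itself. That is right, provided the cumulative table is labelled as such and is not the main by-arm comparison. The SAP does not say this.

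**Conclusion.** The point holds in a limited form. The SAP plans a separate post-challenge summary, but followed as written its Day 1-to-end-of-study by-arm summaries mix exposures after Day 85. This goes beyond a missing detail, because SAP 9.2 and the opening of SAP 9 give instructions that cannot both apply to the same table. The reference dose for time since vaccination and the classification of a child given two different vaccines are also undefined.

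With 40 Boostrix-arm participants, about one sixth of that arm's planned follow-up comes after BPZE1. The figure depends on uptake by arm, which the documents do not give, and on full follow-up. It falls to about 13% if all 40 doses are deferred by 20 days. The affected endpoints are descriptive, so no hypothesis test, power figure or success criterion changes. The primary safety endpoint, solicited events through 7 days after the first vaccination, is untouched. The risk is a misleading summary table, not lost data or an untraceable case.

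**What to change.** Amend SAP 9.2, 9.2.1 and 9.2.4 to 9.2.6, and the matching table shells, as follows:

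- For substudy participants, end the first-vaccination by-arm tables (SAEs, AESIs and SARS-CoV-2, MAAEs, and the unrestricted TEAE rows) at the actual time of the Day 85 BPZE1 dose.
- Report later events in the post-challenge table by Day 1 arm, with every column labelled as BPZE1-exposed. State in SAP 4.3.1 that this is how children given Boostrix and then BPZE1 are classified.
- Count time since vaccination from the most recent study vaccination.
- Keep any uncensored Day 1-to-end-of-study table only as a supplement labelled cumulative.
- State in a footnote how many children per arm leave the main table at the Day 85 dose, because participation is voluntary and uptake may differ by arm.

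The cost is SAP wording and table programming, with no new data. The downside is small: participants contribute about 12 weeks (84 days) instead of 24 (168 days) to the main table, and their later follow-up is reported in the post-challenge table.

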2.3 Other Exploratory Objectives and Endpoints

Other Exploratory Objectives	Other Exploratory Endpoint(s)

 To assess cellular-mediated response (by ELISpot or flow cytometry) to BPZE1 and Boostrix (Th1 and Th2) in a subset of subjects. 	
 Cellular-mediated response at baseline and Day 8 (safety lead-in cohort) and Days 85 and 113 (subset of substudy subjects).

 To further characterize mucosal and serum immunological responses over time, relative to baseline status and to vaccination response, with any future assays developed for BPZE1. 	
 Immunologic response measurement by treatment group.

3 Investigational Plan

3.1 Study Design

This is a multi-centre, randomized, observer-blinded, placebo- and active comparator-controlled trial with a 6-month safety follow-up after first study vaccination. After signing the informed consent form (ICF; or providing assent when necessary) and meeting all inclusion and none of the exclusion criteria, eligible subjects will receive an intranasal vaccination with either BPZE1 vaccine or formulation buffer (placebo) via the MAD and an intramuscular (IM) injection of either Tdap vaccine (i.e., Boostrix) or sterile normal saline (placebo) on Day 1. To maintain the blind, placebo vaccination via intranasal and IM routes, using formulation buffer and normal saline, respectively, will be included, and an unblinded team will manage vaccine logistics, preparation, and administration (when needed to maintain blinding) but will not be involved in study-related assessments or have subject contact for data collection after study vaccination.

Approximately 360 subjects will be enrolled and randomly assigned (1:1:1) to 1 of 3 treatment groups (refer to Table 3-1) to contribute to safety and efficacy assessments. Enrolment will be operationally managed at the study level to maintain a minimum number of subjects enrolled in 2 age groups: 6 to 10 years, inclusive; and 11 to 17 years, inclusive. It is estimated that a 10% dropout rate will occur, allowing for approximately 108 evaluable subjects per treatment group.

Table 3-1 Dosing Scheme

Treatment Group	n	Intranasal Vaccination ^a (Day 1)		IM Vaccination ^b (Day 1)	
		BPZE1	Placebo	Boostrix	Placebo
A	120	X	-	-	X
B	120	X	-	X	-
C	120	-	X	X	-

^a Intranasal application of ~0.4 mL per nostril (0.8 mL total volume delivered). Intranasal vaccination will occur prior to IM vaccination.

^b IM injection of 0.5 mL to the deltoid region.

All subjects will be monitored for at least 30 minutes after final study vaccination. On Day 1, intranasal vaccination will occur prior to IM vaccination with a minimum of 10 minutes (minimum of 30 minutes for subjects in the safety lead-in cohort of 11 to 17 year olds)

between intranasal and IM vaccinations. Immediate reactogenicity will be assessed at 30 minutes (+30 minutes) after the last study vaccination of the Day (ie, after IM vaccination on Day 1, after nasal vaccination on Day 85), prior to release from clinical observation.

All subjects will record maximum daily reactogenicity in a subject diary for 7 consecutive days starting the day following any study vaccination (retrospective of the highest value in the previous 24 hours). Subject diaries will be age-adjusted as appropriate. Local (arm; after IM injection only), nasal/respiratory, and general systemic reactogenicity events will be recorded, including start and stop dates and including any actual measurements (ie, body temperature, redness and/or swelling at the injection site). Trained clinical staff will review the information from the subject diary with the subjects at the following visit and apply a standard toxicity grade to any reactogenicity event. Subjects will be instructed that should they have reactogenicity with a potential toxicity grade 3 at any time, they should contact the site on the same day and be seen or referred to a qualified medical facility within 24 hours.

As this is the first study of BPZE1 in school-age children, a staggered enrolment is planned. The first 45 subjects enrolled will be in the older age group (11 to 17 years, inclusive) and designated the safety lead-in cohort. Reactogenicity will be reviewed with these subjects during a supplemental visit 7 days following first study vaccination. After reactogenicity for the safety lead-in cohort is reviewed by the medical monitor, medical lead, and Safety Monitoring Committee (SMC) chairman (with appropriate consultation with investigators, if needed), the remainder of subjects will be enrolled.

All AEs will be monitored through 28 days after any study vaccination; all MAAEs will be monitored through 84 days following any study vaccination; and all AESIs and SAEs will be monitored through Day 169/EOS. Due to COVID-19 pandemic, a SARS-CoV-2 infection (confirmed by testing within the public health system) and any associated symptoms will be collected on a unique COVID-19 electronic case report form (eCRF) through Day 169/EOS if the COVID-19 pandemic remains ongoing in the region or if there are mass vaccinations using a COVID-19 vaccine during study conduct. Vaccines received outside of the study will be specifically queried at each visit and recorded through Day 169/EOS.

An informational card will be provided to all subjects indicating their participation in this vaccination study to prevent subjects from inadvertently receiving any scheduled/planned Boostrix-containing vaccines (tetanus, pertussis, diphtheria) during study conduct. Any

enrolled subject who does not receive Boostrix during the study will be offered Boostrix at the conclusion of the study (following unblinding); this Boostrix ‘catch-up’ will be provided outside of the study schedule, at the discretion of the investigator, with vaccine provided by the sponsor.

Nasal and blood samples for immunogenicity assessments will be collected before vaccination and at selected time points following study vaccination. Mid-turbinate/nasopharyngeal sample collections will occur at selected time points following study vaccination to assess initial colonization (safety lead-in cohort only, Day 8) and to assess for clearance (remainder of cohort, either Day 29 or Day 85). A subset of subjects will also have the option to provide extra blood for cellular-mediated immunity assessments at baseline and Day 8 (safety lead-in cohort) and Days 85 and 113 (subgroup optional in substudy).

Due to the uncertainty with movement and/or isolation practices associated with the COVID-19 pandemic, telemedicine and remote sampling may be initiated with proper investigator and/or medical oversight.

The primary database lock will occur after all data are clean and all planned study procedures through Day 169/EOS (6 months) are complete. An interim database lock may occur after all subjects have completed Day 29 and sample testing for all primary and select secondary immune endpoints have been completed (mucosal and serum), but results will only be provided at treatment assignment level to maintain the blind. The site and those interacting directly with the site or subject data (eg, contract research organization [CRO], laboratories) will remain blinded to subject assignment until EOS or end of sample testing, depending on the activities of the associated entities.

Vaccination pause rules (refer to Section 6.5) will be in place with a review by the SMC initiated if any rule is met. In addition, the medical monitor and medical lead are empowered to request a review by the SMC (refer to Section 11.1.1.1) at any time for any safety reason.

3.1.1 Substudy: Attenuated Challenge With BPZE1 Following Prior Vaccination with BPZE1, BPZE1 + Boostrix, or Boostrix Alone

This is an optional open-label substudy in which enrolled subjects may elect to participate at any time from the day of enrolment through Day 85. A separate signed ICF (and separate

assent when necessary) will be obtained prior to participation in the substudy. Subjects will be excluded from participating in the substudy if they meet additional exclusion criteria listed in Section 4.1.2.1. Temporary vaccination holding criteria are to be followed for the Day 85 vaccination.

Up to 120 enrolled subjects may participate in the substudy. The duration of the entire study will not change; however, additional visits/procedures starting on Day 85 will include the following:

- 3 additional visits (Days 92, 99, and 113)
- 1 additional intranasal vaccination (Day 85)
- Up to 3 additional nasal samples, including 2 of those needed for mid-turbinate/nasopharyngeal sample collection (Days 92 and 99) and 1 needed for leukosorb (Day 113). Subjects will contribute to all Day 85 sampling (systemic and nasal)
- Up to 2 additional blood samples (Days 85 [if not already assigned to provide] and 113, including blood for cellular-mediated and systemic immunity responses)
- 1 additional subject diary (subjects to record maximum daily reactogenicity [nasal/respiratory, systemic] in a subject diary for 7 consecutive days starting the day following study vaccination)
- 1 additional test for SARS-CoV-2 within 72 hours prior to Day 85 vaccination

All subjects participating in the open-label substudy will receive an intranasal re-vaccination/attenuated challenge with BPZE1 on Day 85. Subjects may have the planned re-vaccination/attenuated challenge deferred to a later date (up to 20 days) if pre-defined temporary exclusion criteria are met (Section 4.1.2.1) or for other personal reasons (eg, holiday, school schedule). Subjects will be monitored for at least 30 minutes after re-vaccination/attenuated challenge, with a post-vaccination evaluation for reactogenicity (nasal/respiratory, and systemic) completed prior to release from clinical observation.

Subjects will receive a subject diary on Day 85. All subjects (with assistance when needed) will record maximum daily reactogenicity in a subject diary for 7 consecutive days starting the day following re-vaccination/attenuated challenge (retrospective of the highest value in the previous 24 hours). Subject-reported symptom diaries will be age-adjusted as appropriate.

Nasal/respiratory and general systemic reactogenicity events will be recorded, including measurements of body temperature. Trained clinical staff will review the information from the subject diary with the subjects at the following visit and apply a standard toxicity grade to any reactogenicity event. Subjects will be instructed that should they have reactogenicity with a potential toxicity grade 3 at any time, they should contact the site on the same day and be seen or referred to a qualified medical facility within 24 hours.

Nasal and blood samples for immunogenicity assessments will be collected before re-vaccination/attenuated challenge and at selected time points thereafter. Mid-turbinate/nasopharyngeal sample collections will be performed at selected time points to assess BPZE1 colonization (*B. pertussis* culture or PCR). Some subjects participating in the substudy may also provide extra blood (optional) for cellular-mediated immunity assessments on Day 85 and Day 113 (optional extra blood collection for up to 45 substudy participants).

All AEs will be collected following re-vaccination/attenuated challenge on Day 85 through Day 113. Following Day 113, only MAAEs, AESIs, and SAEs will be collected though Day 169/EOS.

4 Subject Selection and Withdrawal Criteria

